# AIM 1: Determine the impact of timed rectal evacuation on anorectal dysfunction in MS patients

We will conduct a four week, single-center, randomized, double-blind placebo controlled clinical trial designed to assess the efficacy of timed rectal evacuation in improving the subjective global assessment of bowel symptoms in a cohort of patients with mild-to-moderate severity MS disease. Patients will be randomized 1:1 to administer either placebo or bisacodyl 10 mg rectal suppositories every other day during the 4 week trial. The primary endpoint will be the change in patients' rating of bowel symptom severity (10 point rating scale) at end of 4 weeks compared to baseline values. We will define an adequate treatment response as greater than a 30% reduction in symptom severity using an intention-to-treat analysis.

AIM 2: Determine the predictors of treatment response and impacts on quality of life

We plan to collect information on the patients' assessed severity of baseline and treatment-associated anorectal dysfunction, their impact on quality of life, as well as daily bowel diaries. Patients also will undergo anorectal sensory and manometric testing as a part of their routine clinical care. Enrolled patients that complete the study will be assessed for study medication compliance. All of these measures will be used to explore factors that are associated with treatment response. Changes in assessments of anorectal dysfunction-related quality of life will serve as key secondary end-points.

This proposal will significantly advance MS care and management by developing the evidence to support the adoption of a simple, safe, and cost-effective clinical treatment algorithm for anorectal dysfunction in the MS population. This paradigm for anorectal dysfunction management could be applicable to a majority of MS patients, and the treatment algorithm could be introduced to patients by nurses or mid-level clinical providers during points of routine MS patient care. Importantly, the treatment could be effectively accomplished by most patients and their caregivers at home. The findings of this investigation could also have a broader influence on care models for anorectal dysfunction associated with a range of other neurological illnesses, such as Parkinson's Disease, ALS, or stroke.

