RESEARCH PLAN: The goal of this proposal is to determine the efficacy of timed rectal evacuation as a treatment for anorectal dysfunction symptoms in patients with mild-to-moderate severe MS. The primary end-point of the randomized clinical trial is a greater than 30% improvement in patients' subjective global assessment of bowel symptom severity after 4 weeks. In secondary analyses, we will determine the factors predicting treatment response, as well as assess the impact of therapy on measures of global and anorectal dysfunction-related quality of life.

Study Design: This is a single-center, randomized, double-blind placebo controlled trial incorporated into routine clinical care for MS patients with anorectal dysfunction. Patients will be randomized to receive placebo or bisacodyl 10 mg rectal suppositories every other day for 4 weeks.

Study Population and enrollment: Patients at the University of Pittsburgh Medical Center (UPMC) MS Center with anorectal dysfunction will be recruited via either an existing registry, chart review, and/or ongoing care encounters. The UPMC MS Center currently cares for well over 2,000 patients. The study is adequately powered if enrollment reaches 56 patients (see Power Analysis below). To ensure adequate numbers in an intention-to-treat analysis, we will plan for a ~20% patient drop-out rate (thus, enrolling 70 patients in total). Normal clinical care pathways at UPMC naturally generate ~2-3 patient consultations per week for MS patients with anorectal dysfunction (total ~125 patients per year), and the pool of potential study candidates far exceeds that number. Therefore, enrollment of 70 patients appears quite feasible.

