- 2.14.2 Are you requesting a waiver of the requirement to obtain written HIPAA authorization for the collection of the PHI?
  - \* No

[reviewer notes-]

- 2.15 Does this research study involve the long-term storage (banking) of biological specimens?
  - \* No

[reviewer notes¬]

- 2.16 Will research participants be asked to provide information about their family members or acquaintances?
  - \* No

[reviewer notes¬]

2.17 What are the main outcome variables that will be evaluated in this study?

PRIMARY END POINT: The primary end-point of the randomized clinical trial is a greater than 30% improvement in patients' subjective global assessment of bowel symptom severity after 4 weeks based on the answer to the following question: "Using a scale of 1 to 10 (1 being no problem and 10 being maximally impactful symptoms), how would you rate the severity of your bowel symptoms over the past 2 weeks?"

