#### SECONDARY END POINTS:

1) Daily Bowel Diaries – patients will record the consistency (Bristol Stool Scale, 1-7), number of bowel movements (BM), and occurrence of any fecal incontinence (FI) episodes each day. This data will be used to abstract BM and FI weekly frequency, as well as the mean change in stool consistency during the study period.

- 2) Patient Assessment of Constipation Symptom Questionnaire (PAC-SYM)
- 3) Fecal Incontinence Severity Index (FISI)
- 4) Patient Assessment of Constipation QOL (PAC-QOL)
- 5) Rockwood Fecal Incontinence Quality of Life Scale (FIQL)
- 6) SF-36 health status questionnaire
- 7) Study Medication Compliance
- 8) Anorectal Sensory and High Resolution Anorectal Manometry Testing: First sensation of rectal filling, urgency, and pain, basal anal resting pressure, voluntary anal squeeze pressure, and the rectal-anal inhibitory reflex (RAIR) to rectal distention and simulated strain, as well as the ability to evacuate a 50 cc volume rectal balloon within one minute.
- 2.18 Describe the statistical approaches that will be used to analyze the study data.
  - \* Addressed below:

Categorical data will be analyzed using Fisher's Exact tests for differences in proportions. Continuous data will be analyzed using Student's t-tests to detect differences in group means, with Bonferroni correction for multiple comparisons. We will use logistic regression to determine the factors that predict treatment responses.

A p<0.05 will be used as the threshold for statistical significance in all cases.

POWER ANALYSIS/SAMPLE SIZE: It is generally regarded that a 3-point reduction represents a clinically meaningful change using such a 10 point scale, and similar research studies using patient-reported outcomes have reported standard deviations ranging around ~2.5 points. However, we do not have baseline data to estimate variance, and thus we took a conservative estimate with an expected standard deviation of 4 points. Given these assumptions, we will need 28 patients in each study arm to detect at least a 30% reduction in symptom severity, with a power of 0.80, alpha=P<0.05 in a two-tailed analysis.

[reviewer notes-]

- 2.19 Will this research be conducted in (a) a foreign country and/or (b) at a site (e.g., Navajo Nation) where the cultural background of the subject population differs substantially from that of Pittsburgh and its surrounding communities?
  - \* No

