3.8 Does this research study involve neonates of uncertain viability or nonviable neonates?

\* No

[reviewer notes¬]

- 3.9 Fetal Tissues: Does this research involve the use of fetal tissues or organs?
  - \* No

[reviewer notes¬]
--->

3.10 What is the total number of subjects to be studied at this site, including subjects to be screened for eligibility?

Note: The number below is calculated by summing the data entered in question 3.11. Any additions or changes to the values entered in 3.11 will be reflected in 3.10.

- \* 400
- 3.11 Identify each of the disease or condition specific subgroups (include healthy volunteers, if applicable) that will be studied.

Click on the "Add" button and specify for each subgroup:

- 1) how many subjects will undergo research related procedures at this site; and
- 2) if applicable, how many subjects will be required to undergo screening procedures (e.g., blood work, EKG, x-rays, etc.) to establish eligibility. Do Not include subjects who will undergo preliminary telephone screening.

\*

Subgroup	Number to undergo research procedures	Number to undergo screening procedures
View MS patients	70	400

- 3.12 Provide a statistical justification for the total number of subjects to be enrolled into this research study at the multicenter sites or this site.
  - \* Described below:

The primary outcome measure is the group mean difference in subjective severity ratings of bowel symptoms using a 10 point scale. It is generally regarded that a 3-point reduction represents a clinically meaningful change using such a scale, and similar

Section: Section 3 - Human Subjects

research studies using patient-reported outcomes have reported standard deviations ranging around ~2.5 points on a 10 point scale. However, we do not have baseline data in this population to estimate variance, and thus we took a conservative estimate with an expected standard deviation of 4 points. Given these assumptions, we will need 28 patients in each study arm to detect at least a 3 point reduction in symptom severity, with a power of 0.80, alpha=P<0.05 in a two-tailed analysis.

Thus, the study is adequately powered if enrollment reaches 56 patients. However, to ensure adequate numbers in an intention-to-treat analysis, we will plan for a ~20% patient drop-out rate. Therefore, we will aim to enroll 70 patients in total.

[reviewer notes¬]

3.13 Inclusion Criteria: List the specific criteria for inclusion of potential subjects.

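### Section 2.18 claims 80% power for a 30% reduction with 28 per arm, but that number was derived for a 3-point mean difference, as section 3.12 says

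*Combined protocol and SAP*

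**What the plan says.** Section 2.18 opens its power paragraph with an effect in points: "It is generally regarded that a 3-point reduction represents a clinically meaningful change using such a 10 point scale". It takes an SD of 4 as a conservative choice, against about 2.5 in similar studies, and says there are no baseline data from which to estimate variance. From these assumptions it concludes: "we will need 28 patients in each study arm to detect at least a 30% reduction in symptom severity, with a power of 0.80", at two-sided alpha 0.05.

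Section 3.12 repeats the same assumptions and ends differently: "we will need 28 patients in each study arm to detect at least a 3 point reduction in symptom severity". It also names the quantity being powered: "The primary outcome measure is the group mean difference in subjective severity ratings of bowel symptoms using a 10 point scale".

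Elsewhere the plan uses 30% as a threshold for improvement:

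- Aim 1 (section 1.2) measures the rating on a "10 point rating scale) at end of 4 weeks compared to baseline values" and adds: "We will define an adequate treatment response as greater than a 30% reduction in symptom severity".
- Section 2.17 defines the primary endpoint as "a greater than 30% improvement in patients' subjective global assessment of bowel symptom severity after 4 weeks based on the answer" to the 1-to-10 severity question. Section 2.6 states the same threshold.
- Section 2.6 then says: "The study is adequately powered if enrollment reaches 56 patients (see Power Analysis below"). The heading it points to is in section 2.18.

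**The concern.** One sample size, with one SD, power and alpha, is given for two different effects. Three points is an absolute difference in means. A 30% reduction, in the sense the plan uses elsewhere, is relative to baseline, and as an endpoint it is a per-patient response. The two coincide only under a condition that the plan does not state.

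This matters because of how the sections connect. A reader of 2.6 sees a primary endpoint of more than 30% improvement, is told that 56 patients are enough, and is sent to the power analysis. There 2.18 offers 80% power for a 30% reduction, phrased almost like the endpoint. The natural conclusion is that the trial has 80% power for its primary endpoint, and no calculation in the plan supports that. Power for a mean reduction of 30% needs a baseline mean. Power for the responder endpoint needs a response rate in each arm. The plan gives neither.

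**Working it through.** **Inputs from the documents.** Difference 3 points, SD 4, power 0.80, two-sided alpha 0.05 (2.18 and 3.12); 1:1 allocation (Aim 1); 28 per arm; 56 raised to 70 for about 20% drop-out, i.e. 56 / 0.8 = 70, or 35 per arm if all are analysed (2.6 and 3.12); SD of about 2.5 in similar studies (2.18). Mean baseline and response rates: not given.

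**Step 1: reproduce the 28.** For two means,

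n per arm = 2 × [(z₀.₉₇₅ + z₀.₈₀) × SD / difference]² = 2 × [(1.960 + 0.842) × 4 / 3]² = 27.9, so 28.

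The two-sample t-test (noncentral t) has power 78.7% at 28 per arm and 87.1% at 35. A one-sided test (22 to 23 per arm), a one-sample calculation (16) and SD 2.5 (11 to 12 per arm) do not give 28. The number belongs to 3 points with SD 4.

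**Step 2: the baseline at which 30% has 80% power.** A 30% reduction from mean baseline B is 0.3 × B points, so B = (detectable difference) / 0.3. Detectable differences are for 80% t-test power.

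| SD | n per arm | Detectable difference (points) | Baseline needed |
|---|---|---|---|
| 4 | 28 | 3.05 | 10.2 (10.0 by normal approximation) |
| 4 | 35 | 2.72 | 9.1 |
| 2.5 | 28 | 1.91 | 6.4 |
| 2.5 | 35 | 1.70 | 5.7 |

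The first row is the plan's own calculation. A mean of 10 on a 1-to-10 scale requires every patient to score the maximum.

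**Step 3: power for a 30% mean difference at lower baselines.** Baselines of 6, 7 and 8 are assumptions. They correspond to differences of 1.8, 2.1 and 2.4 points (two-sided t-test).

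| SD | n per arm | Baseline 6 | Baseline 7 | Baseline 8 |
|---|---|---|---|---|
| 4 | 28 | 38% | 49% | 60% |
| 4 | 35 | 46% | 58% | 70% |
| 2.5 | 28 | 75% | 87% | 94% |
| 2.5 | 35 | 84% | 93% | 98% |

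**Step 4: the responder reading.** Steps 2 and 3 concern a difference in means, not the per-patient endpoint of 2.17. For that endpoint the plan's test is Fisher's exact test (2.18, categorical data). Placebo response rates of 20%, 30% and 40% are assumptions. By exact enumeration at two-sided p<0.05, 80% power needs:

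| Placebo response | Active response, 28 per arm | Difference | Active response, 35 per arm | Difference |
|---|---|---|---|---|
| 20% | 58.9% | 39 points | 54.0% | 34 points |
| 30% | 70.4% | 40 points | 66.2% | 36 points |
| 40% | 79.1% | 39 points | 75.3% | 35 points |

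Section 5.16 counts patients who withdraw after Phase 1 as non-responders. With all 70 analysed, the 35-per-arm differences would have to hold after that dilution. The table shows what a supported claim would have to state; it does not estimate this trial's power.

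**The case against.** The strongest defence is that 30% is shorthand for 3 points on a 10-point scale. The paragraph in 2.18 starts from 3 points and derives its 28 from that premise. Section 3.12, the form's designated place for justifying the sample size, repeats the paragraph with the 3-point wording, and it also carries the 56 and the step to 70. A careful reader can recover the intended effect, and no number in the plan is miscalculated. The low power figures above also depend on an SD that the plan itself calls conservative; at 2.5 most of the grid exceeds 80%.

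Much of this stands. The shorthand reading is plausible, the sample size is right for 3 points, and the SD 2.5 rows show why the claim is unsupported rather than false. But neither section says that 30% means 3 of 10 points, and Aim 1, 2.6 and 2.17 use 30% for something else. Section 2.6 directs the reader by heading to 2.18, not to 3.12. If the phrase is shorthand, the same correction is needed.

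It is also fair to say that correcting one phrase does not settle which primary outcome the plan intends: Aim 1, 2.6 with 2.17, and 3.12 describe it differently. That is a separate matter. It does not make the power statement in 2.18 correct.

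**Conclusion.** The concern holds. In 2.18 the figure of 28 per arm with 80% power is attached to an effect for which it was not calculated. It is valid for a 3-point difference in group means with SD 4 (80% by the normal approximation, 79% by the t-test). If 30% is relative to baseline, the claim at the planning SD and 28 per arm needs a mean baseline of about 10. If 30% is the responder threshold, the plan contains no power calculation for it.

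The power percentages for 30% rest on assumed baselines and the responder figures on assumed placebo rates, since the documents give neither. They do not show that the trial is too small. What fails is the stated power claim. It should be corrected because the plan's own cross-reference presents it as support for the primary endpoint.

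**What to change.** In 2.18, replace the 30% reduction in the power sentence with the 3-point reduction of 3.12, and say that it is a difference in group means. Claim 80% power for a 30% mean reduction only if the assumed mean baseline and SD are given. Claim it for the endpoint of more than 30% improvement only if the assumed response rate in each arm is given. The adequacy statement in 2.6 should be read under the same conditions, because it follows that endpoint and relies on 2.18.

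The cost is one phrase. Sample size, endpoint and procedures do not change. The only loss is a more modest power statement, since the plan could no longer claim 80% power for a 30% reduction.

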# **Section 3 - Human Subjects**

3.1 What is the age range of the subject population?

18-80

- 3.2 What is their gender?
  - \* Both males and females

Provide a justification if single gender selected:

- 3.3 Will any racial or ethnic subgroups be explicitly excluded from participation?
  - \* No

If **Yes**, identify subgroups and provide a justification:

- 3.4 For studies conducted in the U.S., do you expect that all subjects will be able to comprehend English?
  - \* Yes

[reviewer notes¬]

- 3.5 Participation of Children: Will children less than 18 years of age be studied?
  - \* No

If **No**, provide a justification for excluding children:

Multiple sclerosis does not typically manifest in childhood. Childhood MS may represent a variant of the disease not generalizable to the typical adult MS population.

[reviewer notes¬]

- 3.6 Does this research study involve prisoners, or is it anticipated that the research study may involve prisoners?
  - \* No

[reviewer notes¬]

- 3.7 Will pregnant women be knowingly and purposely included in this research study?
  - \* No

[reviewer notes¬]

3.8 Does this research study involve neonates of uncertain viability or nonviable neonates?

\* No

[reviewer notes¬]

- 3.9 Fetal Tissues: Does this research involve the use of fetal tissues or organs?
  - \* No

[reviewer notes¬]
--->

3.10 What is the total number of subjects to be studied at this site, including subjects to be screened for eligibility?

Note: The number below is calculated by summing the data entered in question 3.11. Any additions or changes to the values entered in 3.11 will be reflected in 3.10.

- \* 400
- 3.11 Identify each of the disease or condition specific subgroups (include healthy volunteers, if applicable) that will be studied.

Click on the "Add" button and specify for each subgroup:

- 1) how many subjects will undergo research related procedures at this site; and
- 2) if applicable, how many subjects will be required to undergo screening procedures (e.g., blood work, EKG, x-rays, etc.) to establish eligibility. Do Not include subjects who will undergo preliminary telephone screening.

\*

Subgroup	Number to undergo research procedures	Number to undergo screening procedures
View MS patients	70	400

- 3.12 Provide a statistical justification for the total number of subjects to be enrolled into this research study at the multicenter sites or this site.
  - \* Described below:

The primary outcome measure is the group mean difference in subjective severity ratings of bowel symptoms using a 10 point scale. It is generally regarded that a 3-point reduction represents a clinically meaningful change using such a scale, and similar

Section: Section 3 - Human Subjects

research studies using patient-reported outcomes have reported standard deviations ranging around ~2.5 points on a 10 point scale. However, we do not have baseline data in this population to estimate variance, and thus we took a conservative estimate with an expected standard deviation of 4 points. Given these assumptions, we will need 28 patients in each study arm to detect at least a 3 point reduction in symptom severity, with a power of 0.80, alpha=P<0.05 in a two-tailed analysis.

Thus, the study is adequately powered if enrollment reaches 56 patients. However, to ensure adequate numbers in an intention-to-treat analysis, we will plan for a ~20% patient drop-out rate. Therefore, we will aim to enroll 70 patients in total.

[reviewer notes¬]

3.13 Inclusion Criteria: List the specific criteria for inclusion of potential subjects.

MS patients with mild to moderately severe disease (MSIS-29 Physical domain scores <61 or an equivalent EDSS < 6.5) aged 18-80, of any gender, disease subtype, duration of illness, or with any current use of disease modifying therapy and who also have anorectal dysfunction (chronic constipation and/or fecal incontinence) are eligible. MSIS-29 and EDSS scores are determined in the course of routine MS care at UPMC.

3.14 Exclusion Criteria: List the specific criteria for exclusion of potential subjects from participation.

MS patients with severe disease, as assessed by MSIS-29 Physical domain scores greater than 61 or an equivalent EDSS of greater than 6.5), aged <18 or >80, or patients with surgically altered anorectal anatomy (i.e. proctectomy/partial colectomy, ostomy creation), active enteric infection (i.e. Clostidium Difficile), or inflammatory bowel disease (i.e. ulcerative proctitis) will be excluded.

3.15 Will HIV serostatus be evaluated specifically for the purpose of participation in this research study?

\* No

If **Yes**, provide a justification:

Section: Section 4 - Recruitment and Informed Consent Procedures

[reviewer notes¬]

**4.1** Select all recruitment methods to be used to identify potential subjects: Research Registry

Other Strategies: Described below

# Research Registry

List the IRB approval number and title for each registry source: PRO12010609: "UPMC Multiple Sclerosis and Related Disorders Registry"

4.2 Provide a detailed description of your recruitment methods, including identifying and initiating contact with participants:

Patients at the University of Pittsburgh Medical Center (UPMC) MS Center with anorectal dysfunction will be recruited via two possible mechanisms: 1) via an existing MS research registry of patients who have previously expressed a willingness to participate in research projects and/or 2) during the course of ongoing, routine clinical care encounters at the UPMC MS Center.

Patients identified by method 1 or 2 will be contacted either in person or by phone during business hours by our study coordinator. We may send an email announcement of the study to the patients on the MS research registry.

The UPMC MS Center currently cares for well over 2,000 patients and generates ~125 outpatient consultations per year to the NeuroGI group (PI/Co-PI) to help co-manage MS patients with anorectal dysfunction. We should not have difficulty meeting our target enrollment for the study.

Note: Questions jump from 4.2 to 4.6 as questions 4.3-4.5 have been removed and the information is now captured in 4.1

[reviewer notes¬]

4.6 Are you requesting a waiver to document informed consent for any or all participants, for any or all procedures? (e.g., a verbal or computerized consent script will be used, but the subjects will not be required to sign a written informed consent document. *This is not a waiver to obtain consent.* 

\* No

[reviewer notes-]

4.7 Are you requesting a waiver to obtain informed consent or an alteration of the informed consent process for any of the following?

\* No

4.7.1 If Yes, select the reason(s) for your request:

There are no items to display

General Requirements: The Federal Policy **[45 CFR 46.116 (d)]** specifies in order for a waiver of consent to be approved, the request must meet four criteria. For each request, you will be asked to provide a justification addressing how each of these criterion is met.

[reviewer notes¬]

4.8 Are you requesting an exception to the requirement to obtain informed consent for research involving the evaluation of an 'emergency' procedure?

**Note:** This exception allows research on life-threatening conditions for which available treatments are unproven or unsatisfactory and where it is not possible to obtain informed consent.

\* No

[reviewer notes-]

4.9 Upload all consent documents for watermarking:

Draft Consent Forms for editing:

Name Modified Date

Consent Form 10/26/2018 10:02 AM

Approved Consent Form(s):

Name Modified Date

Consent Form 10/26/2018 10:02 AM

[reviewer notes¬]

4.10 Will all potential adult subjects be capable of providing direct consent for study participation?

\* Yes

[reviewer notes¬]

4.11 At what point will you obtain the informed consent of potential research subjects or their authorized representative?

After performing certain of the screening procedures, but prior to performing any of the research interventions/interactions

4.11.1 Address why you feel that it is acceptable to defer obtaining written informed consent until after the screening procedures have been performed.

Study flow will be optimized by making an assessment of inclusion and exclusion criteria before approaching patients; there is no benefit to obtaining written informed consent in an individual not eligible for the study, and there wasted time and effort (for both patient and investigative team) in doing so. There is no appreciable harm (i.e. HIPPA will be preserved) if our study coordinator pre-screened patients with upcoming appointments to

the UPMC MS center. Lastly, the most substantial screening will be performed using an already IRB-approved MS patient registry designed specifically for this purpose (PRO12010609, "UPMC Multiple Sclerosis and Related Disorders Registry").

4.11.2 Taking into account the nature of the study and subject population, indicate how the research team will ensure that subjects have sufficient time to decide whether to participate in this study. In addition, describe the steps that will be taken to minimize the possibility of coercion or undue influence.

The patients enrolled via the MS patient registry or those identified by screening the list of patients with upcoming MS clinic visits will have several days to even weeks before deciding to participate in the study. Patients identified by MS care physicians during the course of routine care are already referred to the PI/Co-PI. These referrals could trigger an inquiry into their interest in study participation. Due to the schedules of the PI/Co-PI, these consultations often are scheduled at least 6-8 weeks prior to being seen. Thus, there should be ample time for participants to consider their decision to enroll in the study. Our study coordinator will contact patients by phone and present the study paradigm in a non-judgmental way, emphasizing that the decision to enroll will in no way influence their access to care. Additionally, at the point of first contact, patients will not have direct interaction with the PI / Co-PI, and thus there is no clear way that the PI/Co-PI could exert coercion on potential study candidates at that early point.

[reviewer notes-]

